10.12 APPENDIX 12 GUIDELINES FOR THE MANAGEMENT OF TUMOR LYSIS SYNDROME (TLS)

TLS is a metabolic derangement that is the result of rapid destruction of tumor cells. TLS is common in hematological malignancies and can cause several side effects; some of them may become life-threatening. Early recognition of TLS and initiation of therapy is essential.

Intravenous hydration is recommended for all participants prior to start of SAR444245 infusions and is left to Investigator judgment for further cycles.

The participants at greatest risk of TLS are those with a high tumor burden prior to treatment. These patients should be monitored closely, and appropriate precautions should be taken (such as use of prophylactic uric acid lowering agents (eg, allopurinol or rasburicase) and regular measurement of electrolytes.

This appendix provides parameters to be checked in case of TLS suspicion and recommendations for TLS management. Abnormalities listed in this appendix do not exclusively support TLS diagnosis and any differential diagnosis also needs to be assessed, if appropriate.

TLS may present with laboratory parameters changes, clinical manifestations, or both as indicated in [Table 13](#).

Table 13 - Tumor lysis syndrome definitions**Table I. Cairo-Bishop definition of laboratory tumour lysis syndrome.**

Uric acid	$x \geq 476 \text{ } \mu\text{mol/l}$ or 25% increase from baseline
Potassium	$x \geq 6.0 \text{ mmol/l}$ or 25% increase from baseline
Phosphorous	$x \geq 2.1 \text{ mmol/l}$ (children), $x \geq 1.45 \text{ mmol/l}$ (adults) or 25% increase from baseline
Calcium	$x \leq 1.75 \text{ mmol/l}$ or 25% decrease from baseline

Modified from Hande and Garrow (1993).

Laboratory tumour lysis syndrome (LTLS) is defined as either a 25% change or level above or below normal, as defined above, for any two or more serum values of uric acid, potassium, phosphate, and calcium within 3 d before or 7 d after the initiation of chemotherapy. This assessment assumes that a patient has or will receive adequate hydration (\pm alkalinization) and a hypouricaemic agent(s).

Table II. Cairo-Bishop definition of clinical tumour lysis syndrome.

- (1) Creatinine*: $x \geq 1.5 \text{ ULN}^\dagger$ (age >12 years or age adjusted)
- (2) Cardiac arrhythmia/sudden death*
- (3) Seizure*

Modified from Hande and Garrow (1993).

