Clinical tumour lysis syndrome (CTLS) assumes the laboratory evidence of metabolic changes and significant clinical toxicity that requires clinical intervention. CTLS is defined as the presence of LTLS and any one or more of the above-mentioned criteria.

*Not directly or probably attributable to a therapeutic agent (e.g. rise in creatinine after amphotericin administration).

† Creatinine levels: patients will be considered to have elevated creatinine if their serum creatinine is 1.5 times greater than the institutional upper limit of normal (ULN) below age/gender defined ULN. If not specified by an institution, age/sex ULN creatinine may be defined as: $> 1 < 12$ years, both male and female, $61.6 \text{ } \mu\text{mol/l}$; $\geq 12 < 16$ years, both male and female, $88 \text{ } \mu\text{mol/l}$; ≥ 16 years, female, $105.6 \text{ } \mu\text{mol/l}$; ≥ 16 years, male, $114.4 \text{ } \mu\text{mol/l}$.

For participants in the safety run-in or participants who are hospitalized because of high tumor burden or at Investigator's discretion, tumor lysis laboratory tests (corrected calcium, magnesium, phosphate, uric acid, and lactate dehydrogenase [LDH] levels) will be obtained per details provided in the individual substudy).

Cardiac monitoring and admission to the ICU is required if TLS is established, as well as continuing laboratory monitoring every 4-6 hours. Additional measures to treat metabolic derangements associated with TLS may be required, as shown in [Table 14](#).

Prophylaxis against TLS may be required depending on the patient's risk for TLS, as described below.

Low-risk is defined as:

- Patients with low tumor burden (WBC $\leq 50 \times 10^9/l$ and normal LDH level)
- Patients receiving low intensity cytoreductive therapy
- Normal pre-existing uric acid
- Adequate hydration
- No tumor infiltration in the kidney

High-risk is defined as:

- Hematological malignancies with high proliferative rate
- High tumor burden (WBC $\geq 50 \times 10^9/l$ and high LDH level)
- Elevated uric acid level
- Patients receiving intensive cytoreductive therapy
- Poor hydration
- Leukemia infiltration of the kidney

Recommendations for **intravenous hydration** during SAR444245 treatment in patients at high risk for TLS, include the following:

- [REDACTED]
- [REDACTED]
- [REDACTED]
- [REDACTED]

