For high risk patients, prophylactic treatment with **allopurinol** should begin 2 to 3 days before the start of antineoplastic therapy and continue for 10 to 14 days, as described in [Table 15](#).

Rasburicase is indicated for patients with the following features:

- High-risk of TLS development
- Urgent need to initiate therapy in a patient with a high bulk of malignant disease
- In a situation where adequate hydration may be difficult or impossible
- Acute renal failure

The dose for rasburicase is indicated in [Table 15](#). Redosing must be individualized.

Recommendations regarding the selection of allopurinol and/or rasburicase are summarized in [Table 16](#).

Table 14 - Specific recommendations for treatment of TLS

Hyperphosphatemia: ≥ 2.1 mmol/L	Removing phosphates from i.v. solutions Oral phosphate binders: e.g. aluminum hydroxide orally at 50-150 mg/kg/24 h q6h Peritoneal dialysis, hemodialysis or continuous venovenous hemofiltration may be required in a case of severe hyperphosphatemia. Calcium infusion is prohibited!
Hypocalcemia: ≤ 1.75 mmol/L (serum) or ionized calcium is \leq of ionized local limit	Treatment not required if asymptomatic. Symptomatic hypocalcemia (muscle cramps and spasms, paresthesias, arrhythmias, heart block, hypotension, confusion, delirium, hallucination, seizures) requires treatment: Calcium gluconate 50 – 100 mg/kg/dose i.v.
Hyperkalemia	Moderate and asymptomatic (≥ 6.0 mmol/L): Avoid i.v. and oral potassium ECG and cardiac rhythm monitoring Sodium polystyrene sulphonate 1 g/kg with 50 % sorbitol po or per rectum Severe (>7.0 mmol/L) and/or symptomatic Same as above, plus Calcium gluconate (100–200 mg/kg) i.v. and/or Regular insulin (0.1 unit/kg i.v.) + D25 (2 mL/kg) i.v. Dialysis
Renal dysfunction (uremia)	Fluid and electrolyte management Uric acid and phosphate management Adjust renally excreted drug doses Dialysis (hemo- or peritoneal) Hemofiltration (CAVH, CVVH, CAVHD or CVVHD)
Hyperuricemia: uric acid ≥ 476 μmol/L	See Table 15 and Table 16 regarding selection and dose of hypouricemic agents: Allopurinol Rasburicase (recombinant urate oxidase).

Table 15 - Recommendations on the use of hypouricemic agents**Allopurinol**

100 mg/m²/dose q8 h (10 mg/kg/d divided q8 h) p.o.
(maximum 800 mg/d) or 200–400 mg/m²/d in 1–3 divided doses i.v. (maximum 600 mg/d)
Reduce dose by 50% or more in renal failure
Reduce 6-mercaptopurine and/or azathioprine doses by 65–75% with concomitant allopurinol

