- g Weight/Height: Height is required at baseline only for patients > or =18 years old. For trial participants <18 years old, height should be assessed on day 1 \pm 1 of each cycle. Weight is required at Screening and prior to starting each infusion. The total dose will be calculated based on the weight on the day of the infusion or the most recent weight assuming it was assessed in a reasonable time frame according to Investigator assessment. Study sites should make every effort to measure body weight as close to the infusion day as possible considering the variability of local process from site to site. If the infusion is prepared with the most recent weight assessed in a reasonable time frame, this will not prevent to assess the weight on D1 of each cycle.
- h Blood chemistry/ hematology will be performed weekly on D1 pre-dose, D8 and D15 during Cycle 1, then on Day 1 of every cycle up to Cycle 12, then every other cycle during Treatment Phase. Visits and assessments on C1D2-D3 are only for participants in the safety run-in or participants who are hospitalized because of high tumor burden or at investigator's discretion. For these participants, vital signs, SpO₂ and complete blood counts (CBC) and differentials, chemistries (blood urea nitrogen (BUN), creatinine (Cr), alanine transaminase (ALT), aspartate transaminase (AST), alkaline phosphatase (Alk Phos), total bilirubin (TBil) will be obtained daily.
- i Tumor lysis laboratory tests (corrected calcium, magnesium, phosphate, uric acid, and lactate dehydrogenase [LDH] levels) will be obtained every 8 hours on C1D1 for safety run-in participants or participants who are hospitalized, and C1D2-D3 for safety run in or participants who are hospitalized because of high tumor burden or at investigator's discretion.
- j Endocrine function tests will be performed every 2 cycles throughout the entire treatment period and at EOT. During the Observation Period, they will be performed at Follow-Up Visit 1. They can also be performed as clinically indicated.
- k Coagulation includes international normalized ratio (INR), prothrombin time (PT) and activated partial thromboplastin time (aPTT).
- l Urinalysis will be performed on C1D1 and C2D1, then as clinically indicated during the treatment period, and will be performed at Follow-Up Visit 1.

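### The 8-hourly tumor lysis panel omits potassium, one of the four analytes that define laboratory TLS, so some cases may be recognised late; uric acid also has no scheduled value before C1D1

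*Protocol*

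**What the plan says.** **The panel.** Master protocol Section 10.12 lists the tests and leaves their timing to the substudies: "tumor lysis laboratory tests (corrected calcium, magnesium, phosphate, uric acid, and lactate dehydrogenase [LDH] levels) will be obtained per details". Footnote i of Section 1.3 in Substudies 01 and 03 sets the frequency: "Tumor lysis laboratory tests (corrected calcium, magnesium, phosphate, uric acid, and lactate dehydrogenase [LDH] levels) will be obtained every 8 hours". Substudy 01 Section 6.5.4.7 and Substudy 03 Section 6.5.4.6 repeat the list. All five statements name the same five analytes, without potassium. The two Section 6.5.4 paragraphs then include potassium among the abnormalities to be corrected if TLS occurs.

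**The definition.** Table 13 in Section 10.12 requires a 25% change or an out-of-range level "for any two or more serum values of uric acid, potassium, phosphate, and calcium within 3 d before or 7 d after" the start of treatment. Magnesium and LDH, which are on the panel, are not part of the definition.

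**Routine chemistry.** Master Table 6 (Section 10.2) includes potassium and does not include uric acid. The Schedule of Activities grid marks blood chemistry on C1D1, D2 and D3 and points to Section 10.2. Footnote h gives a shorter list for D2 and D3 (BUN, creatinine, ALT, AST, alkaline phosphatase, total bilirubin).

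**Who is covered on D2 and D3.** Footnote e restricts these visits to run-in participants. Footnotes h, i and o, and Table 6 note a, also bring in participants hospitalized with a high tumor burden.

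**Uric acid.** The tumor lysis row of the grid is marked on C1D1 to D3 and not at screening. Section 10.12 nevertheless uses uric acid before treatment: "Elevated uric acid level" is a high-risk feature, and Table 16 uses the level to choose between allopurinol and rasburicase.

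**The concern.** The panel is the only intensive laboratory surveillance scheduled around the first dose, and it leaves out one of the four values needed to apply the protocol's own definition. Because the same paragraphs call for potassium to be corrected, the omission looks like an oversight.

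What is at stake is how soon TLS is recognised. Clinical TLS in Table 13 presupposes laboratory TLS. Once TLS is established, Section 10.12 requires cardiac monitoring, ICU admission and "continuing laboratory monitoring every 4-6 hours". Hyperkalemia also has action levels of its own in Table 14. From 6.0 mmol/L the entry reads "Avoid i.v. and oral potassium ECG and cardiac rhythm monitoring", and above 7.0 mmol/L it extends to dialysis.

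For uric acid, the concern is that risk is assigned, and prophylaxis chosen, with one listed input not scheduled in time.

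**Working it through.** The plan gives no figure to reproduce. The check is a count of combinations followed by a comparison of schedules.

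**1. Inputs.** Defining analytes (Table 13): uric acid, potassium, phosphate, calcium. Panel (five statements): calcium, magnesium, phosphate, uric acid, LDH. Overlap: three of the four defining analytes.

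**2. Qualifying combinations.** Two or more of four: C(4,2) + C(4,3) + C(4,4) = 6 + 4 + 1 = 11.

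**3. Established from the panel alone.** At least two of the three overlapping analytes must be abnormal, with potassium either normal or abnormal: (C(3,2) + C(3,3)) × 2 = (3 + 1) × 2 = 8. Not established: 11 − 8 = 3, namely potassium with uric acid, with phosphate, or with calcium. Among the 6 pairs alone, these are 3.

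**4. Any warning from the panel.** Each of the 3 combinations contains exactly one panel analyte, so the panel shows at least one abnormality in 11 of 11.

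**5. Potassium sampling on C1D1 to D3.** There are two readings.
- Grid plus Table 6: potassium about once every 24 h, against every 8 h for the other three analytes, a ratio of 24 / 8 = 3. The D1 chemistry is pre-dose, so the first scheduled post-dose potassium is on D2.
- Footnote h taken as the complete D2-D3 list: no potassium on those days, and the next scheduled value is on D8.

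Table 6 note a supports the first reading. It is attached to the chemistry row that contains potassium, and it says the C1D2-D3 assessments are done. Footnote h does not say that its list replaces Table 6. The first reading is the better supported, but the text is not clean.

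**6. Uric acid timing.** Footnote a allows baseline tests within 7 days before the first dose, D-7 to D-1. Section 10.12 has allopurinol start 2 to 3 days before therapy in high-risk patients. Assuming a same-day result, a draw on D-7 to D-2 (6 of 7 days) leaves at least 2 days, a draw on D-7 to D-3 (5 of 7) leaves 3, and a draw on D-1 leaves neither. At present no draw is required on any of these days. Participants who are neither in the run-in nor hospitalized have no scheduled uric acid at all.

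**7. After the change.** With potassium on the panel, all 11 combinations can be established from it.

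**The case against.** The strongest reply is that the panel is surveillance and was never meant to be the whole diagnosis. Section 10.12 says of itself: "This appendix provides parameters to be checked in case of TLS suspicion and recommendations for TLS management". For participants with a high tumor burden it advises "regular measurement of electrolytes", and Table 6 note a allows chemistry whenever clinically indicated. An abnormal uric acid, phosphate or calcium should raise suspicion and prompt a potassium test. This largely stands, and it sets the size of the point. A reader might infer from the 3-of-6 pair count that half the definition goes undetected. The documents do not support that, because every one of those cases shows an abnormal panel analyte and potassium is also in routine chemistry. What the reply does not supply is a required potassium at the panel's frequency.

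A reader might also infer that potassium is not measured on D2 and D3. The grid, Table 6 and its note a point the other way; footnote h only makes this ambiguous.

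On uric acid, a reader might infer that a result is needed at least 3 days before C1D1. The protocol says 2 to 3 days, and only for allopurinol. Table 16 directs an elevated uric acid to rasburicase, for which no lead-in is stated. Footnote a has results reviewed before dosing, so a pre-dose C1D1 value could still guide that choice in run-in and hospitalized participants. The timing argument is therefore limited to keeping allopurinol possible.

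**Conclusion.** The omission is real and appears in all five panel statements. Laboratory TLS made up of potassium plus exactly one other analyte, 3 of the 11 qualifying combinations, cannot be established from the 8-hourly panel alone. Recognition then waits for roughly daily chemistry, or for a discretionary test prompted by the single abnormal panel analyte. The consequence is possible delay in starting the escalated care.

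This assumes that the panel lists are complete as written and that sites draw what is scheduled. The counts are combinations, not probabilities. Master Section 2.3.1.2.1 reports no preclinical TLS data for SAR444245, and the documents give no TLS rate for it, so the number of participants affected cannot be estimated.

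The uric acid gap is secondary: one listed input to risk and agent choice is not scheduled before C1D1, while the other listed features remain available. The footnote e conflict is an inconsistency to tidy. None of this touches the primary endpoint or any planned analysis.

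**What to change.** 1. Add potassium to the tumor lysis test list in master Section 10.12, footnote i of Section 1.3 in both substudies, Substudy 01 Section 6.5.4.7 and Substudy 03 Section 6.5.4.6.
2. Make the C1D2-D3 chemistry in footnote h match Table 6, so that daily potassium is explicit.
3. Align footnote e with footnotes h, i and o and Table 6 note a, so that participants hospitalized with a high tumor burden are covered on D2 and D3.
4. Add uric acid to the screening chemistry within the existing 7-day baseline window, preferably with the result at least 2 days before C1D1 so that the allopurinol lead-in stays possible. A fixed 3-day rule is not needed.

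The cost is amendment wording and a little more laboratory data entry. Potassium is run on blood already being drawn every 8 hours, and uric acid on the screening chemistry sample. A site that draws its screening chemistry on D-1 would be encouraged to draw uric acid earlier.

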1.4 BIOMARKER FLOWCHARTS

1.5 PHARMACOKINETIC FLOWCHARTS

Cycle	Treatment Cycle 1					Treatment Cycle 2, 4, 7, 10 + every 5 th cycle		EOT visit	
Day	D1			D2	D3	D8	D1		30 (± 7) days after last IMP administration
Time after start of SAR444245 dosing [h]	SOI	EOI	4h post EOI	At any time	At any time	At any time	SOI	EOI	At any time
SAR444245 PK sample		P00 ^b	P01	P02 ^c	P03 ^c			P00 ^b	
SAR444245 ADA sample	AB00 ^a					AB01	AB00 ^a		ABF00

a Samples collected strictly before start of infusion (SOI). ADA sampling may be discontinued by the Sponsor once sufficient data have been collected.

b PK sample must be taken at the end of infusion (EOI) after flush.

c P02 and P03 to be collected during safety run-in and when participants are hospitalized.

In the event the infusion is interrupted, a PK sample should be drawn immediately after interruption. If infusion is not likely to be resumed by clinical assessment, subsequent samples should be drawn at 4 h after interruption. If infusion is resumed, a (further) PK sample should be drawn at end resumed infusion and subsequent sample should be drawn at 0.5 h after end of resumed infusion. PK sampling may be discontinued by the Sponsor once sufficient data have been collected.

Abbreviations: ADA: anti-drug antibodies; D: day; EOT: end of treatment; PK: pharmacokinetic.

2 INTRODUCTION

Study ACT16941 is developed as a master protocol in order to accelerate the investigation of SAR444245 with or without various anticancer therapies by identifying early signals. The information that is common to all cohorts is included in the master protocol, and this substudy provides details specific to Cohort A (participants with cHL who are anti-PD-(L)1-naïve and have received at least 2 or 3 lines of systemic therapy) for the combination therapy with pembrolizumab.

Please refer to the master protocol for an introduction for ACT16941.

2.1 STUDY RATIONALE

Preclinical studies demonstrated that treatment with SAR444245 leads to polyclonal expansion of CD8+ T cells in murine and NHP models while anti-PD1 antibody prevents T cell suppression through the PD1/PD-L1 pathway. The combination of anti-PD1 treatment with SAR444245 was tested in a syngeneic mouse CT-26 colon cancer model and demonstrated enhanced anti-tumor activity and prolonged survival compared to each monotherapy. These data support evaluation of SAR444245 in combination with pembrolizumab.

2.2 BACKGROUND

2.2.1 Pembrolizumab

Pembrolizumab is a potent humanized immunoglobulin G4 (IgG4) monoclonal antibody (mAb) with high specificity of binding to the programmed cell death protein 1 (PD1) receptor, thus inhibiting its interaction with programmed cell death ligand 1 (PD-L1) and programmed cell death ligand 2 (PD-L2). Based on preclinical in vitro data, pembrolizumab has high affinity and potent receptor blocking activity for PD1. Pembrolizumab has an acceptable preclinical safety profile and is in clinical development as an IV immunotherapy for many advanced malignancies. Keytruda® (pembrolizumab) is indicated for the treatment of patients across a number of indications, including as monotherapy for relapsed or refractory cHL or PMBCL. For more details on specific indications refer to the pembrolizumab Investigator's Brochure (IB).

Refer to the approved local labeling for detailed background information on pembrolizumab.

2.2.1.1 *Pharmaceutical and therapeutic background*

The importance of intact immune surveillance function in controlling outgrowth of neoplastic transformations has been known for decade (3). Accumulating evidence shows a correlation between tumor-infiltrating lymphocytes (TILs) in cancer tissue and favorable prognosis in various malignancies. In particular, the presence of CD8+ T-cells and the ratio of CD8+ effector T cells/FoxP3+ regulatory T-cells (T-regs) correlates with improved prognosis and long term

survival in solid malignancies, such as ovarian, colorectal, and pancreatic cancer; hepatocellular carcinoma; malignant melanoma; and renal cell carcinoma (RCC). Tumor-infiltrating lymphocytes can be expanded ex vivo and reinfused, inducing durable objective tumor responses in cancers such as melanoma (4, 5).

The PD1 receptor-ligand interaction is a major pathway hijacked by tumors to suppress immune control. The normal function of PD1, expressed on the cell surface of activated T cells under healthy conditions, is to down-modulate unwanted or excessive immune responses, including autoimmune reactions. PD1 (encoded by the gene *Pdcd1*) is an immunoglobulin (Ig) superfamily member related to cluster of differentiation 28 (CD28) and cytotoxic T-lymphocyte-associated protein 4 (CTLA-4) that has been shown to negatively regulate antigen receptor signaling upon engagement of its ligands (PD-L1 and/or PD-L2) (6, 7).

The structure of murine PD1 has been resolved (8). PD1 and its family members are Type I transmembrane glycoproteins containing an Ig-variable type (IgV type) domain responsible for ligand binding and a cytoplasmic tail responsible for the binding of signaling molecules. The cytoplasmic tail of PD1 contains 2 tyrosine-based signaling motifs, an immunoreceptor tyrosine-based inhibition motif, and an immunoreceptor tyrosine-based switch motif. Following T-cell stimulation, PD1 recruits the tyrosine phosphatases, SHP-1 and SHP-2, to the immunoreceptor tyrosine-based switch motif within its cytoplasmic tail, leading to the dephosphorylation of effector molecules such as CD3 zeta (CD3 ζ), protein kinase C-theta (PKC θ), and zeta-chain-associated protein kinase (ZAP70), which are involved in the CD3 T-cell signaling cascade (7, 9, 10, 11). The mechanism by which PD1 down-modulates T cell responses is similar to, but distinct from, that of CTLA-4, because both molecules regulate an overlapping set of signaling proteins (12, 13). As a consequence, the PD 1/PD-L1 pathway is an attractive target for therapeutic intervention in cHL.

